### **10.2** Sample Size Considerations

We will use a mixed longitudinal model for our primary analyses (see Statistical Analyses below). Since some aspects of the model such as covariance structure are unknown, we performed power and sample size calculations using a more conservative, simplified model corresponding to a two-group t-test on change scores. We plan to analyze two co-primary outcome measures: the ABC-SW, which will provide consistency with pivotal trials of other medications hypothesized to improve ASD social symptoms, and the combined social score, which integrates ABC-SW symptoms with the new Pervasive Developmental Disorders Behavior Inventory-Screening Version SOCDEF raw score (PDDBI-SV, Cohen 2011, also see Outcome Measures) in order to fully capture the range of impairments in reciprocal social behaviors observed in ASD. We will use an alpha of 0.025 to correct for two co-primary outcomes. SOARS-B is powered for Aim 1b to allow independent evaluation of oxytocin efficacy in low and high-functioning youth.

Standard deviations of change scores for the ABC-SW range from ~5 to 9 in several large ASD intervention trials (McCracken, McGough et al. 2002; Shea, Turgay et al. 2004; Aman, McDougle et al. 2009; [name], Hollander et al. 2009; Marcus, Owen et al. 2009; Owen, [name] et al. 2009). We consider a between groups difference of 5-7 points in ABC-SW change scores to be clinically meaningful. In our power calculations, we use conservative estimates of 9 points for the SD of ABC-SW change and 5 points for between group differences in ABC-SW changes (differential improvement on  $\sim 1/3$  of items). To achieve 80% power with an alpha of 0.025 on the ABC-SW, we will require 71 participants in each treatment group within the two strata. Thus, our total required sample for the ABC-SW in Aim 1b is 284. We examined change in the combined social score in 30 3-17 year olds with ASD, 20 treated with aripiprazole and 10 medication-free controls. The mean baseline value was 33.5 (17.2 SD) and the change overall was -10.7 (SD 13.0), with a SD of change in each group of 11.9. Within each treatment group, changes in the combined social score paralleled those in the ABC-SW and PDDBI-SV, but had less variability ([name], personal data). We consider a between groups difference in the combined social measure changes of 10-12 to be clinically meaningful. Conservative estimates using a SD of 15 and a between groups difference of 10 in the combined social score changes results in a larger effect size for the combined social measure than for the ABC-SW. Consequently, we should have at least 80% power. A sample size of 300 will allow for 5% attrition between randomization and the first post-randomization visit. On 3/28/2016 we reduced the attrition rate to 1% based on attrition rate observed to date which gives a final sample size of 290. Aims 1a, 3 and 4 consider all participants, resulting in much greater power than for Aim 1b. The power of moderator analyses depends on the distribution of participant characteristics and variability in methylation and mRNA expression observed, which can't be estimated reliably at this time.

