**ABC-SW Total** 

Sociability Factor (SF)

The SF will be calculated by discarding the three lethargy items (3, 32, 53) from the ABC-SW, summing the 13 remaining items of the ABC-SW subscale, and adding the sum to the PDDBI-SV raw social deficits score.

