### 2.2 General Summarization of Study Data

Unless otherwise specified, continuous variables will be summarized with descriptive statistics including n, mean, standard deviation (SD), median, first quartile (Q1) and third quartile (Q3) and minimum and maximum values. Categorical variables will be reported as number and percentage of participants in each category. Least squares (LS) means, standard errors, estimates of contrasts with 95% confidence intervals (CI), and p-values will be reported as appropriate.

All other statistical tests and confidence intervals will be 2-sided, unadjusted for multiplicity, and tested at  $\alpha$  = 0.05, except those explicitly stated to be otherwise.

All analyses and summaries will be produced using SAS® version 9.3 (or higher).

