#### 6. SAMPLE SIZE AND STATISTICAL POWER CONSIDERATION

We will use a mixed longitudinal model for our primary analyses (see Efficacy Analyses section). Since some aspects of the model such as covariance structure are unknown, we performed power and sample size calculations using a more conservative, simplified model corresponding to a two-group t-test on change scores. SOARS-B is powered to allow independent evaluation of oxytocin efficacy in low and high-functioning youth.

Standard deviations of change scores for the ABC-SW range from  $^{\sim}5$  to 9 in several large ASD intervention trials (Shea 2004; McCracken 2002; Owen 2009; Marcus 2009, [name] 2009; Aman 2009). We consider a between groups difference of 5-7 points in ABC-SW change scores to be clinically meaningful. In our power calculations, we use conservative estimates of 9 points for the SD of ABC-SW change and 5 points for between group differences in ABC-SW changes (differential improvement on  $^{\sim}1/3$  of items). To achieve 90% power with an alpha of 0.05 on the ABC-SW, we will require 71 participants in each treatment group within the two strata. Thus, our total required sample to evaluate the ABC-SW separately in low and high-functioning strata is 284. A sample size of 300 will allow for 5% attrition between randomization and the first post-randomization visit. On 3/28/2016, the study team reduced the attrition rate to 1% based on attrition observed in the study, which gives a final sample size of 290. The primary objective considers all participants, resulting in much greater power than for analyses in separate strata.

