## 2.2 Study Outcome Measures

#### 2.2.1 **Primary Outcome Measures**

Our primary outcome is reciprocal social behaviors, which we will assess using two co-primary measures. The first measure is the ABC-SW subscale, which is being used in other clinical trials focusing on the core social and communication symptoms of autism. The other measure is the

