Sociability Factor (SF), a combined measure derived from 13 items of the ABC-SW, which primarily captures aloof, and avoidant behaviors, and the Pervasive Developmental Disorders Behavior Inventory-Screening Version (PDDBI-SV, Cohen 2011), a recently developed measure which assesses both maladaptive social problems and social skills. The PDDBI-SV is comprised of 18 items included in the older, more comprehensive Pervasive Developmental Disorders Behavior Inventory (PDD-BI, Cohen 2003). The PDDBI-SV assesses both social impairments typically associated with the active but odd subtype of ASD and development of pro-social skills that are integral to improved reciprocal social behavior. The PDDBI-SV results in a raw SOCDEF score, which is the sum of the reverse-scored social skills and the regularly-scored problems, and a SOCDEF T score. In marked contrast to the PDD-BI's age-based standard scores (for children 1.5 and 12.5 years old), the PDDBI-SV SOCDEF score does not change with age in individuals with ASD. The PDDBI-SV has been validated in original PDD-BI development sample of 311 children 1-17 years old and a recently-acquired sample that includes 145 youth between 13 and 15 years old, 90 between 16 and 19 years, and 59 between 20 and 40 years (Cohen 2011, personal communication). The sociability factor SF will be calculated by discarding the three lethargy items from the ABC-SW (questions 3, 32, and 53, which all assess reduced physical movement), summing the 13 remaining items of the ABC-SW subscale, and adding it to the PDDBI-SV raw SOCDEF score. The sociability factor SF is derived from two well-validated instruments and has face validity for capturing the full range of impairments in reciprocal social behaviors observed in ASD. We chose not to use the Social Responsiveness Scale (SRS), which was developed to provide a quantitative measure of social impairments typically observed in ASD in children 3-18 years old, because it has been demonstrated to be quite stable over time (Constantino, Przybeck et al. 2000; Constantino 2009) and no intervention studies have clearly demonstrated its sensitivity to change.

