#### **Outcome Measures:**

 Initially planned to have two co-primary outcomes, the ABC-SW and a combined measure later termed the Sociability Factor, later discontinued this in the final SAP though change was not formally made in protocol.

- At one point added the cyberball social exclusion task as an objective measure that had shown sensitivity to change with oxytocin in single dose studies; later eliminated it because we were not able to adapt for use with younger children, individuals with intellectual disability or a racially diverse sample with automated scoring.
- Removed w24 ADOS due to financial constraints and lack of evidence of change previously
- Required collection of study specific genetic measures but not NIMH repository samples
- Added optional PK sample at target and maximal dose per FDA request
- Added cognitive testing as an outcome at week 24 (after initially also including week 48 and 72)
- Added salivary oxytocin collection at same times as plasma oxytocin collection
- Specified key secondary outcomes for analysis 1c
- Removed PDD-BI full version and switched to 18 item PDD-BI-SV to reduce participant burden
- Switched from Vineland Interview version to Vineland caregiver-report version to reduce burden on staff and participants.

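### Protocol 10.2 ties 71 per arm per stratum to 80% power at alpha 0.025, but its own inputs need 63 (71 gives 85%) and the final SAP attaches the same 71 to a different alpha and power; separately, protocol and 2021 clarification disagree on whether items 3, 32 and 53 belong to the primary ABC-SW

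*Combined protocol and SAP*

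**What the plan says.** **Sample size.** Protocol v6.0, section 10.2, plans two co-primary outcomes ("We will use an alpha of 0.025 to correct for two co-primary outcomes") and sizes the study with a two-group t-test on change scores, using a difference of 5 and an SD of 9 on the ABC-SW. It concludes: "To achieve 80% power with an alpha of 0.025 on the ABC-SW, we will require 71 participants in each treatment group", in each of two functioning strata, or 284 in all. The same sentence stands in the original protocol (v1.0, section 10.2) and in SAP v1.0.

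The final SAP (v2.0), section 6, keeps the difference, the SD and the 284, but has a single primary and reads: "To achieve 90% power with an alpha of 0.05 on the ABC-SW, we will require 71 participants in each treatment group". Its section 2.2 sets the sidedness: "All other statistical tests and confidence intervals will be 2-sided, unadjusted for multiplicity". The high-level summary of protocol changes says of the co-primary design that the team "later discontinued this in the final SAP though change was not formally made in protocol".

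**Scored items.** Protocol v6.0, section 2.2.1, introduces the primary score thus: "The first measure is the ABC-SW subscale, which is being used in other clinical trials". It then forms the Sociability Factor by "discarding the three lethargy items from the ABC-SW (questions 3, 32, and 53, which all assess reduced physical movement), summing the 13 remaining items" and adding the PDDBI-SV raw score. SAP v1.0 has the same construction: "discarding the three lethargy items (3, 32, 53) from the ABC-SW, summing the 13 remaining items of the ABC-SW subscale". The final SAP's abbreviation list names the Social Withdrawal subscale without modification. Its section 4.1.1 names the ABC-SW score and lists no items, and section 4.1 sends the reader to the protocol for descriptions. The clarification dated 05-15-2021 says that ABC-SW meant, throughout protocol and SAP, a version without items 3, 32 and 53, and it makes the original subscale a sensitivity analysis.

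**The concern.** The two points are independent.

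First, the final protocol and the final SAP attach one sample size to two different alpha and power pairs with the same effect size. Both can be literally true only in the sense that 71 meets or exceeds each target. As statements of what is required, they cannot both follow from the same inputs. A reader who tries to verify the protocol's justification will fail.

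Second, the trial has one confirmatory test, on the ABC-SW at week 24. If the protocol implies one item set and a document written alongside the primary paper states another, the definition of that endpoint cannot be traced through the dated plan. The Sociability Factor uses the same 13 items on either reading; only the primary score changes.

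**Working it through.** **Part 1: sample size**

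Inputs: difference δ = 5, SD σ = 9, two-group t-test, alpha 0.025, 80% power (protocol 10.2); 1:1 allocation (SAP 1.3); two-sided testing (SAP 2.2; the protocol section does not state it). The standardised difference is d = 5/9 = 0.556.

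Normal approximation, per arm: n = 2(z₁₋α/₂ + z₁₋β)²σ²/δ², with 2σ²/δ² = 2 × 81/25 = 6.48.

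- Protocol pair (0.025, 80%): (2.241 + 0.842)² × 6.48 = 61.6, so 62.
- Final SAP pair (0.05, 90%): (1.960 + 1.282)² × 6.48 = 68.1, so 69.

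Exact t-test power uses the noncentral t with 2n − 2 degrees of freedom and noncentrality δ/(σ√(2/n)). At n = 71 the noncentrality is 5/(9 × √(2/71)) = 3.31.

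| Test | n per arm per stratum | Power |
|---|---|---|
| two-sided 0.025 | 62 | 79.4% |
| two-sided 0.025 | 63 | 80.1% |
| two-sided 0.025 | 71 | 85.1% |
| two-sided 0.05 | 71 | 90.8% |

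The protocol's 71 is therefore not reproduced: 63 suffice, and 63 × 4 = 252 against 71 × 4 = 284. The SAP's figure is reproduced within rounding (70 are needed for 90% at two-sided 0.05).

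Other readings that might yield 71 at 80%:

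- One-sided alpha 0.025 needs 52.
- Two-sided alpha 0.0125 (a second halving, stated nowhere) needs 74; 71 gives 78.1%.
- Inflating 63 for the stated 5% attrition gives 63/0.95 = 66.3, so 67. The plan in any case applies attrition after 284: 284/0.95 = 299 (stated 300) and 284/0.99 = 287 (stated 290).
- At two-sided 0.025, 71 is exactly the t-test requirement for 85% power. That 85% was intended is a guess; no text says so.

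Because the sentence already stood in the first protocol and first SAP, the 80% was never right for these inputs. Only the alpha became out of date when the co-primary was dropped. The SAP change list (item 24) reports the removal of the second primary but not the move from 80% to 90%.

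The effect is confined to the stratum analyses (Aim 1b). With 142 per arm in the whole sample, power at two-sided 0.05 is 99.7%.

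**Part 2: item set**

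| Source | What it implies for the primary ABC-SW |
|---|---|
| Protocol v6.0, 2.2.1 | Items 3, 32 and 53 are taken out of the ABC-SW only to form the Sociability Factor, leaving 13; the ABC-SW itself has 13 + 3 = 16 |
| SAP v1.0, primary efficacy variables | Same construction, with the ABC-SW total listed separately |
| Final SAP, abbreviations, 4.1 and 4.1.1 | Unmodified subscale name, no item list, refers to the protocol |
| Final SAP, 4.4 | Only the per-protocol sensitivity analysis |
| Clarification, 05-15-2021 | 13 items throughout; original subscale is a sensitivity analysis |

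Items can be discarded from a scale only if the scale contains them, so the protocol's natural reading contradicts the clarification. Neither the SAP change list nor the outcome-measures part of the protocol change summary records a removal of items from the primary.

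**The case against.** On the sample size, the strongest reply is that nothing depends on it. Seventy-one does deliver at least 80% at alpha 0.025; the fault lies in calling it required. Protocol 10.1 points to the SAP, the procedural-changes summary says the SAP holds the final plan, and the sponsor discloses that the co-primary change never reached the protocol. The SAP's own figure is sound. SAP 2.2 also speaks of other tests, so it does not cleanly settle sidedness for the primary. All of this stands as a limit on the point's weight. It does not make 71 the 80% answer under either sidedness, and the disclosure explains the alpha, not the power.

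On the items, the reply is that the clarification is part of the package: it tells the reader which items were scored and why, and it lists the original-subscale analysis. No document states 16 items; that is inferred from 13 + 3. The final SAP's own text is compatible with either reading, so the conflict is between the protocol and the clarification. Whether the 13-item set was fixed before unblinding cannot be decided from these documents, and nothing here shows a post hoc change. These limits also stand. What remains is that the clarification postdates the final SAP (2-19-2018), cites no earlier record of the item set, and contradicts the protocol to which the SAP refers.

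**Conclusion.** Both points hold.

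The protocol's size statement is wrong as written: 63 rather than 71 per arm per stratum for 80% at two-sided alpha 0.025, or 85.1% rather than 80% at 71. It conflicts with final SAP section 6, whose pair is correct. This rests on the documents' difference, SD and t-test, and on two-sided testing. The error is conservative and is a matter of reconciliation only.

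The item-set conflict carries the weight, because it concerns the score behind the only confirmatory test: three items are in on the protocol's natural reading and out on the 2021 clarification, 16 against 13. The 16 is an inference from wording. No effect on power is claimed, and no conclusion is drawn about when the 13-item definition was adopted.

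**What to change.** 1. In protocol 10.2, replace the power statement so that it agrees with SAP section 6: ABC-SW as sole primary, two-sided alpha 0.05, 71 per arm per stratum giving about 91% power. Remove the co-primary wording from 2.2.1 and the co-primary and alpha 0.025 wording from 10.2.
2. List the scored items of the primary ABC-SW in SAP 4.1.1 and protocol 2.2.1, and add the original-subscale analysis to the sensitivity analyses in SAP 4.4.
3. Cite the dated record that fixed the item set. If none exists from before unblinding, state that the 13-item definition was set down after the final SAP, and report results for both scores.

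The cost is wording only. Both scores come from the same completed ABC form, and the original-subscale analysis is already listed in the clarification, so no further participants or data are needed.

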## 11 SUBJECT CONFIDENTIALITY

In order to protect confidentiality, only randomly assigned ID numbers rather than names will appear on clinically sensitive charts, files, and digital data. The key linking the numeric identifier and participant's identity will be maintained on a separate drive that is double password protected and to which only the site PI and coordinator have access. Contact information will be recorded separately in double password protected files with restricted access as above. The code linking the names with

the ID numbers will be securely protected with limited access. Medical records will be kept confidential with access granted only to those medical and research professionals directly involved with the study. If any scientific paper based on the data collected for this study is published, no information that could be linked to any single participant will be reported. Confidentiality will be protected to the fullest extent permitted by law. All research personnel have completed HIPPA training for researchers and human ethics training.

The samples for the methylation portion of the study (which will be sent to [name]'s team at Duke) will be single-coded, that is, labeled with a single specific code that does not carry any personal identifiers. Single coding is the current standard used in clinical research and offers additional safeguards to the subject's identifiers compared to the HIPAA authorization. With this method it is possible to trace the samples back to a given subject with the use of the single coding key. The clinical study investigator is responsible for maintaining the coding key. This coding key will be stored separately from the research data. When stored electronically, it will be password protected as it will contain identifying information. The samples will also note the date of collection and visit number.

# 13 APPENDIX A (Clinical Parameters for Cardiac Monitoring)

# **BLOOD PRESSURE PARAMETERS FOR GIRLS**

AGE	MIN	MIN	MAX	MAX
	(5th % height)	(95th % height)	(5th % height)	(95th % height)
3	86/47	93/51	104/65	110/69
4	88/50	94/54	105/68	112/72
5	89/52	96/56	107/70	113/74
6	91/54	98/58	108/72	115/76
7	93/55	99/59	110/73	116/77
8	95/57	101/60	112/75	118/78
9	96/58	103/61	114/76	120/79
10	98/59	105/62	116/77	122/80
11	100/60	107/63	118/78	124/81
12	102/61	109/64	119/79	126/82
13	104/62	110/65	121/80	128/83
14	106/63	112/66	123/81	129/84
15	107/64	113/67	124/82	131/85
16	108/64	114/68	125/82	132/86
17	108/64	115/68	125/82	132/86

#### **BLOOD PRESSURE PARAMTERS FOR BOYS**

AGE	MIN (5th %	MIN (95th %	MAX (5th %	MAX (95th %
	height)	height)	height)	height)
3	86/44	95/48	104/63	113/67
4	88/47	97/52	106/66	115/71
5	90/50	98/55	108/69	116/74
6	91/53	100/57	109/72	117/76
7	92/55	101/59	110/74	119/78
8	94/56	102/61	111/75	120/80
9	95/57	104/62	113/76	121/81
10	97/58	106/63	115/77	123/82
11	99/59	107/63	117/78	125/82
12	101/59	110/64	119/78	127/83
13	104/60	112/64	121/79	130/83
14	106/60	115/65	124/80	132/84
15	109/61	117/66	126/81	135/85
16	111/63	120/67	129/82	137/87
17	114/65	122/70	131/84	140/89

Adapted from National High Blood Pressure Education Program Working Group on High Blood Pressure in Children and Adolescents: The fourth report on the diagnosis, evaluation, and treatment of high blood pressure in children and adolescents(Falkner, Daniels et al. 2004).

#### HEART RATE PARAMETERS

AGE	MIN	MAX
1-3	90	150
4-5	65	135
6-8	60	130
9-11	60	110
12-16	60	110
>16	60	100

Adapted from Pediatric cardiology for practitioners(Park 2008) and Normal ECG standards for infants and children(Davignon, Rautaharju et al. 1979).

#### 14 SUMMARY OF PROTOCOL CHANGES

## **Summary of Changes (Protocol version date 08 March 2013):**

- Removal of whole blood serotonin collection at Months 8, 12, and 18
- Addition of salivary oxytocin collection at same time points as plasma oxytocin collection (Screening, Month 2, Month 6, Month 8, Month 12 and Month 18) (added to schedule of events and in visit descriptions)
- Addition of intelligence tests (Stanford-Binet 5/Mullen at Months 6, 12, 18 (added to Schedule of Events and in visit descriptions)
- Clarified scoring procedures on the Mullen assessment regarding when to calculate mental age for participants
- Revised Oxytocin Flexible Dosing Strategy (Table 3)
- Updated/clarified definitions and recording requirements for concomitant medications. Made clarifications regarding the documentation of PRNs
- Added specific list of prohibited meds (ones that affect brain serotonin levels)
- Added an additional reportable event section:
  - o serious intentional self-harm/serious suicidal ideation
  - o Pregnancy of subject or a subject's sexual partner
- Revised language regarding study stopping criteria:
- Added language regarding Overall Study Stopping Criteria per DSMB request
- Changed "if moderate or severe adverse events occur that cannot be addressed by dose
  adjustment or addition of concomitant medications" to "if moderate or severe adverse events
  occur that cannot be addressed by dose adjustment or addition of concomitant medications (these
  can be discussed with SC and Medical Monitor. Investigators are encouraged to try dose
  reduction or addition of concomitant medications)."
- Changed "clinical worsening (much worse or very much worse on CGI-I) at two consecutive visits unless explicitly discussed and agreed with SC and Medical Monitor that participant can continue in the study" to "If a subject is worsening clinically (they have score of 6 much worse or 7 very much worse on CGI-I, there has to be a return visit/phone call within 1-2 weeks to re-

visit/re-evaluate with CGI-I. If the subject still has 6 or 7, then case must be discussed with SC and Medical Monitor to get approval for participation to continue."

- Changed reporting rule requirements for UPs,SAEs and other reportable events
- Specified UNC's responsibilities for reporting to specific authorities
- Specified reporting requirements for other site
- Added 2 new categories for severity of an adverse event (to be consistent with NC TraCS DSMB
- Life-threatening: Substantial risk dying or requires intervention to prevent death
- Death related to AE: Subject died as a result of the event, self-explanatory
- Made DSMB section consistent:
- DSMB will meet and review the study 3x/year instead of quarterly as previously indicated
- Clarified definition of Serious Adverse Event
- Updated Tables 1 & 2 regarding Adverse Events
- Updated section regarding randomization method:
- We will randomize centrally, using our data management system. We currently do just that in our multicenter IMPACT trial. When a site needs to randomize a subject, after baseline is assessed, the coordinator opens the Randomization form. This form uses already assessed strata to randomize from the appropriate stratum. We will not stratify by site. We felt that both functional status and age group were more likely to be related to the outcome than site, and there are limits to how many strata we can have. We will stratify by functional status (high or low) and age group (3 age groups), producing 6 strata. [name] will generate a randomization plan for each of the 6 strata, using a permuted block algorithm with randomly selected block sizes of 2 and 4, using SAS. The table will be exported to an Excel file and sent to the data manager, [name]. This can be done without having [name] ever actually see the randomization plan. (He will debug the program and when debugged, run it with a new seed for the random number generator without seeing the results.) [name] will import the randomization plan as a table in Access. The Randomization form will use Visual Basic code and the values of the strata variables to enter the correct subset of the table and choose the first unused treatment. It will generate an ID number and send an email to the appropriate pharmacy, where drug will be assigned.

